2.2.3.2 External Ventricular Drainage Catheters

External ventricular drainage Catheters (Figure 12) are indicated for drainage and monitoring of CSF from the lateral ventricles of the brain. The Catheters may be used to reduce ICP, to monitor ICP, to monitor CSF and in the management of hydrocephalic shunt infections.

The Ventricular Catheters are designed for diverting fluid from the ventricles through a series of drainage holes near the Catheter tip. The Catheters can be inserted into the ventricular cavity with the stainless-steel stylet. A trocar is supplied with the Catheters to facilitate subcutaneous tunneling away from the burr hole. The external portion of the Catheter may be secured to the scalp by the suture collar.

All external ventricular Catheters have markings from 3 to 15 cm \pm 1.5 mm with numbers located at odd markings and dots located at even markings. All Catheters have a radiopaque tip: The Product Code INS-8220 Catheter is barium impregnated and the Product Code INS-4000, INS-4500 and INS-8420 are barium striped. An overview of all EVD Catheters and Accessories is provided in APPENDIX I.

[figure not shown]

Figure 12. External Ventricular Drainage Catheters

2.2.3.3 Codman® EDS 3™ Clear Ventricular CSF Catheter

The Codman® EDS 3™ Clear Ventricular CSF Catheter is indicated for gaining access to the ventricles of the brain. It is a 35cm clear silicone Catheter with a radiopaque strip.

2.2.4 EVD Accessories

2.2.4.1 Pole Mount Assemblies and Accessories

The MoniTorr ICP™ Pole Mount Assembly provides support and alignment for External Ventricular Drainage Systems. The Pole Mount Sliding Bracket can be used with the Integra External Ventricular Drainage Systems and may also be used as a replacement assembly or accessory component (Figure 13). The Pole Mount Sliding Bracket is used to secure the External Ventricular Drainage System to the rail of the Pole Mount Assembly. The Pole Mount Assembly incorporates a removable rail graduated in cm H₂O and/or mmHg, a sliding bracket which facilitates secure attachment of the External Ventricular Drainage System through 2 keyholes located at the top of the system panel, and a pointer that is extendible to approximately 75 cm is attached to the bracket for easy alignment to patient's Foramen of Monro.

[figure not shown]

Figure 13. Pole Mount Assembly

2.2.5 Contraindications

Refer to the Instructions for Use for the contraindications specific for each device.

2.3 Intended Purpose in the post-market clinical follow-up registry

The External Ventricular Drainage Systems and Accessories will be used within label in this registry and the registry is of observational nature. There will be no specific medical or surgical procedures involved in the use of the study device, other than the standard of care. A full description of the medical and surgical procedures related to the External Ventricular Drainage Systems are available in the Instructions for Use.

2.4 Required training and experience

The External Ventricular Drainage Systems and Accessories will be used within label in this registry study. The investigators working with these systems have been previously trained on the use of the devices and should be familiar with their use prior to taking part in this registry study. Integra LifeSciences Corporation does not train, nor dictate, the shunt implantation technique. All investigators must meet certain expectations per Sponsor Standard Operating Procedures (SOPs).

2.5 Device Accountability

Given the post-market design of this registry, no device accountability will be performed for the purposes of this registry study.

2.6 Device Traceability

Devices will be tracked by Model, SKU, and LOT numbers, as applicable, which will be part of the data entered into the database of this registry.

3 OBJECTIVES AND ENDPOINTS

3.1 Primary Objective

The primary objective of this registry is to capture clinical performance data to confirm the continued performance of the External Ventricular Drainage Systems and Accessories.

3.2 Safety Objective

The safety objective of this registry is to capture clinical safety data to confirm the continued safety of the External Ventricular Drainage Systems and Accessories.

3.3 Primary Endpoint

The primary endpoint is anticipated drainage (i.e., observed drainage consistent with the patient's clinical presentation) of cerebrospinal fluid (CSF) in the clinical setting until the EVD System is no longer required.

Note: Excessive drainage (e.g., more than 25 cc every hour) not attributable to the patient's condition, widely variable drainage over time inconsistent with the patient's clinical presentation, drainage levels inconsistent with concurrent neurological exams (e.g., GCS, NIHSS, etc.), and/or documented device deficiencies impacting drainage (e.g., breakage disconnection, etc.) are examples of unanticipated drainage of CSF that will be recorded as Adverse Events.

3.4 Secondary Endpoint

The secondary endpoint is the proportion of patients in whom the CODMAN Cranial Access Kit, when used with appropriate accessories, provided successful access to the intracranial space.

3.5 Tertiary Endpoints

- Number of initial Catheter Insertion Attempts [Time Frame: Implantation of subject] Number of insertions needed to place Catheter.

- Number of days initial Catheter is in place.
- Number of Catheter and/or EVD System replacements during treatment, if applicable.
- Number of Catheter flushing interventions per each Catheter if a replacement Catheter is implanted.
- Length of Catheter Tunneling into the Brain [Time Frame: Implant of subject] Length of tunneling of EVD Catheter in the brain for each analysis population.
- Number of Days with initial Indwelling Catheter [Time Frame: Implant of subjects to the day of explant] Days Catheter was implanted in subjects
- Non-infectious Catheter Failure in the ITT Population [Time Frame: Implant of subject to explant] Reasons for non-infectious Catheter malfunctions in the intent to treat population.
- CSF daily drainage.

3.6 Safety Endpoints

1. Device- or procedure-related adverse events (AEs) during the use of the device in the patient.
2. Noted Device Deficiencies during use of the device such as malfunction, use errors, or other issues related to the performance or safety of the External Ventricular Drainage Systems and Accessories.

4 RISKS AND BENEFITS OF THE REGISTRY STUDY

4.1 Anticipated Clinical and Device Benefits

There are no anticipated clinical benefits for the patient as a result of participation in this registry. An increased review of a patient's procedural and follow-up data in addition to standard of care may be beneficial to the patient but is not guaranteed.

4.2 Anticipated Adverse Device Effects/Residual Risks

The External Ventricular Drainage Systems and Accessories will be used according to standard of care. Expected side-effects for patients participating in this registry are therefore not different than expected side-effects without participation.

4.3 Risks Associated with Participation in the Registry study

The External Ventricular Drainage Systems and Accessories will be used within label in this registry study and the study is of observational nature. Patients will not be asked to change their medical or medication treatments other than standard of care. There are no device-related risks for this study. There are, however, privacy (loss of confidentiality) risks associated with participation in the registry.

4.4 Risk Control/Mitigation

This registry does not add any additional risk compared to the risks associated with the use of the External Ventricular Drainage Systems and Accessories outside of this study.

Participation in the study does not submit the patient to any additional procedures or exams outside the customary standard of care. Patient confidentiality and privacy is strictly held in trust by the participating investigators, their staff, and the Sponsor. The patient's data will be given a code in order to assure that the data can only be traced with the use of an identifier. The identifier will be stored securely in the local research institute. Data that is shared with the Sponsor will only contain the code and the name and any other identifiable information will be omitted. Please refer to **Section 12.1.3** for additional information. Therefore, there is no additional risk for taking part in this study.

4.5 Risk/Benefit Analysis

The participation in the registry does not add risks to the patients, thus the benefit is judged to outweigh the overall residual risks.

5 STUDY DESIGN

5.1 Overall Design

The External Ventricular Drainage Post-Market Clinical Follow-Up (PMCF) registry is an observational, multi-center, post-market study.

5.2 Description of Sites

Up to 15 sites in EU countries, UK and Switzerland will participate in this study. Sites will be chosen based upon their experience with the EVD System and accessories and their ability to fulfill general requirements in the Sponsor's SOPs.

5.3 Rationale for Study Design

The purpose of this study is to investigate whether the Integra External Ventricular Drainage Systems listed as part of this registry do perform to clinical expectations.

Additionally, this study will focus on the safety of these devices by collecting any device-specific AEs or DDs seen when used during standard of care procedures.

A registry is the most appropriate design for a study such as this because registries proactively collect study data, but do not needlessly expose patients to non-standard of care interventions or procedures. Additionally, registries include data from patients with complex medical histories which will generally provide more real-world evidence.

Including multiple centers and nations will ensure that data collected is from a broad set of surgeons and countries, thereby increasing the generalizability of the outcomes and conclusions.

Study outcomes will be summarized using descriptive statistics. Categorical variables will be summarized using frequencies and percentages. Continuous variables will be summarized using means, standard deviations, medians, ranges, and numbers of observations.

A sample size of 120 patients will be enrolled for this registry. Inclusion will be halted at sites that reach the 34% (40 subjects) inclusion cap. There will be no minimum number of subjects for a single study site.

Integra LifeSciences Corporation believes this study design and sample size is appropriate to confirm the continued safety and performance of these devices given their well-established nature and the existing clinical evidence base.

5.4 End of Study Definition Overview

The end of the study is defined as completion of case report forms for the last subject in the registry study.

5.5 Primary Study Hypothesis

The primary hypothesis is to evaluate the success rate of CSF drainage against a pre-defined performance goal of 80% (with an expected success rate of 90% or higher). The hypothesis will be tested based on patients of all ages using the exact method along with two-sided 95% confidence interval.

6 STUDY POPULATION

6.1 Inclusion Criteria

In order to be eligible to participate in this study, Patients must meet all of the following criteria:

1. Patient and/or legally authorized representative has agreed to participate in the study by signing the EC-approved consent form, where applicable.
2. Patients (of any age) who underwent or who plan to have a procedure with one of the Integra or Codman External Ventricular Drainage as distributed by Integra System.
3. For patients who have had the EVD System removed prior to study enrollment, have available follow-up data from implant until the EVD System is no longer required for drainage and monitoring of CSF.

6.2 Exclusion Criteria

Patients who meet any of the following criteria will be excluded from participation in this study:

1. The Patients in whom more than one EVD System were or are intended to be placed.
2. The Patient has sepsis.
3. The Patient has a history of poor wound healing.
4. The patient exhibits signs of scalp infection prior to implantation that would be contraindicated per the IFU.
5. The Patient is otherwise determined by the Investigator to be medically unsuitable for participation in this Registry.
6. The Patient is currently enrolled in another device trial or has been previously entered in this trial.
7. The Patient is a prisoner or member of a different vulnerable population that should not be included in the study per the investigator.
8. The Patients known to have uncorrected coagulopathy.
9. The Patients with known hypersensitivity to rifampin or clindamycin hydrochloride (prior to implantation of Bactiseal catheters)

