6.3 Point of Enrollment & Enrollment Period

This is an observational study, and the patients will only provide informed consent to allow use of their data. All consented patients are assigned a study identification (ID) number and screened for eligibility in the study. The study will collect data on each patient from (1) the start of the procedure involving External Ventricular Drainage Systems or Accessories until the EVD System is no longer required for drainage and monitoring of CSF, and (2) in patients who have met all eligibility criteria. Patients eligible for the study are identified and informed consent is obtained prior or after the start of treatment with the devices. In case informed consent is obtained:

- Prior to the start of the treatment with the EVD System and Accessories, the data will be prospectively collected from the implantation procedure until the EVD System is no longer required for drainage and monitoring of CSF.
- After the implantation of the EVD System and Accessories and before the EVD System is no longer required for drainage and monitoring of CSF, the data will be retrospectively collected from the implantation procedure until the point of informed consent and prospectively collected until the EVD System is no longer required for drainage and monitoring of CSF.
- After the EVD System is no longer required for drainage and monitoring of CSF, the data will be retrospectively collected from the implantation procedure until the EVD System is no longer required for drainage and monitoring of CSF.

This registry study is anticipated to have an enrollment period of 25 months.

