6.5 Screen Failures and Failures

Participants who are consented to participate in the registry, who do not meet one or more criteria required for participation in the study during the screening procedures, are considered screen failures.

Participants who underwent or undergo a replacement of the Integra or Codman EVD System with an EVD System other than an Integra or Codman EVD System are considered failures and will be discontinued from the date of the Integra or Codman EVD System replacement. The data collected up to the date of the Integra or Codman EVD System replacement will be included as part of the registry study results, as permitted by national laws and regulations.

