8.2 Performance Data to be Collected

Completion of Worksheets/Case Report Forms (CRFs). Sites will transcribe/transmit the information outlined below in study worksheets and CRFs. This information will originate from existing medical and other patient records.

Patient Data:

- Demographics:
 - Gender
 - Year of Birth (YOB)
- Prescribed clinical diagnosis for CSF drainage (e.g., reason the physician prescribed CSF drainage)

Procedural Data:

- Procedural Information CSF drainage:
 - Dates of EVD System and Accessories placement and removal.
 - Details of Catheter and/or EVD System replacement(s), if applicable.
 - Number of initial Catheter Insertion Attempts i.e., number of insertions needed to place Catheter
 - Length of Catheter Tunneling into the Brain i.e., length of tunneling of EVD Catheter in the brain
 - External Ventricular Drainage System and/or accessories used:
 - Brand name
 - Model, SKU, and LOT number(s), if documented

Clinical Performance Data:

- Daily CSF drainage until the EVD System is no longer required for drainage and monitoring of CSF.
- Intracranial access location
- EVD System and Accessories maintenance procedures
- Number, type, and volume of flush(s) used to address occlusions, if applicable.
- Concomitant neuro-interventional and neurosurgical procedures
- Relevant concomitant medications
- Whether the patient required a permanent shunt after the EVD System is no longer required for drainage and monitoring of CSF, if so (name, model)
- In the case of a malfunctioning EVD system and/or Accessories, the component(s) responsible for malfunction or reason for malfunction (where possible)

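### Does exclusion criterion 1 screen out patients whose EVD System was replaced before consent, whom Protocol 6.5 keeps as failures?

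*Protocol*

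**What the plan says.** Criterion 1, in the synopsis and in Protocol 6.2, bars "The Patients in whom more than one EVD System were or are intended to be placed". It has no words on concurrent systems, initial placement or replacement, and the SAP does not return to it.

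Protocol 6.5 has two rules. Consented participants "who do not meet one or more criteria required for participation in the study during the screening procedures, are considered screen failures". Separately, "Participants who underwent or undergo a replacement of the Integra or Codman EVD System with an EVD System other than an Integra or Codman" system are classed as failures and discontinued at the replacement, and their data up to that date stay in the results.

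Consent can be late. Protocol 6.1 has an inclusion criterion "For patients who have had the EVD System removed prior to study enrollment", and Protocol 6.3 provides for fully retrospective cases: "After the EVD System is no longer required for drainage and monitoring of CSF, the data will be retrospectively collected".

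Replacement is also something the registry sets out to measure. Protocol 3.5 lists "Number of Catheter and/or EVD System replacements during treatment, if applicable" as a tertiary endpoint. Protocol 8.2 collects "Dates of EVD System and Accessories placement and removal" and, as a separate item, "Details of Catheter and/or EVD System replacement(s), if applicable".

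The ITT population and the FAS (Protocol 11.3, SAP 7.3) contain patients considered to meet all criteria, and the PPS requires the same. The primary analysis uses the FAS.

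**The concern.** Criterion 1 and the second rule of 6.5 both reach into the past. Take a patient whose system was exchanged for another make before consent. If a site counts the replacement as a second system, the patient is a screen failure under the first rule of 6.5. Under the second rule the same patient is a failure whose data are kept. A patient with the same course who consented before the exchange would simply stay in.

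Three things would be at stake:

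- Screened-out patients leave the primary denominator. If they fail the primary endpoint more often than others, the success rate is biased upward against the 80% goal.
- System replacements before consent drop out of the tertiary count.
- SAP 8.2.1 asks for reasons only for discontinuations after enrollment, so the loss would be only partly visible in the report.

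A second, smaller question is how a 6.5 failure counts in the primary endpoint. SAP 8.9.1 does not mention 6.5.

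**Working it through.** **1. The text.** The wording of criterion 1 parses most naturally with the intention governing both verbs: more than one system was, or is, intended. An unplanned replacement is then not caught. The looser parse, that more than one system was in fact placed, is possible. The rest of the protocol favours the first:

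| Place | On the planned-systems reading | If a replacement counts as a second system |
|---|---|---|
| Protocol 6.5, second rule | Applies to replacement before and after consent | Its past-tense half has almost nobody left to apply to |
| Protocol 3.5, replacement count | Complete | Loses system replacements made before consent |
| Protocol 8.2, placement and replacement listed separately | Two different events | Distinction blurred |

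**2. Who could be affected.** Protocol 2.2.2 treats catheters as accessories, and Protocol 14.4 lists replacement drainage bags as accessories. Changing either is not a second system. What remains is replacement of the whole system, before consent, at a site that takes the looser parse.

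**3. The plan's own figures.** Inputs: goal 80% and expected rate 90% (Protocol 5.5); 110 evaluable, 80% power, 8% drop-out (Protocol 11.2); success if the exact two-sided 95% lower bound exceeds 80% (Protocol 11.4.3).

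- Lower bound at n = 110: 97 successes give 80.6%, 96 give 79.6%. So 97 are needed.
- P(X ≥ 97 | 110, 0.80) = 1.7%. P(X ≥ 97 | 110, 0.90) = 79.1%, close to the stated 80%.
- 110 / (1 − 0.08) = 119.6, rounded up to 120.

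The sample size is reproduced, and the reading of criterion 1 does not change it.

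**4. Size on the looser parse.** Two assumed quantities are needed: f, the share of all primary-endpoint failures that is screened out across the registry, and q, the share of screened-out patients who are failures. At a true rate of 80%:

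observed rate = (0.8 − 0.2f(1−q)/q) / (1 − 0.2f/q)

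Example, q = 1 and f = 0.05: 0.8 / (1 − 0.01) = 80.8%. Chance of passing at n = 110:

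| q | f = 5% | f = 10% | f = 25% |
|---|---|---|---|
| 1 | 2.8% | 4.4% | 15.5% |
| 0.5 | 2.5% | 3.6% | 10.5% |
| 0.3 | 2.1% | 2.6% | 5.4% |
| 0.2 (overall failure rate) | 1.7% | 1.7% | 1.7% |

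If 2% of all patients are screened out and none is a failure, the observed rate is 0.78/0.98 = 79.6% and the chance is 1.3%. The nominal one-sided 2.5% is crossed at f of about 4.0% (q = 1) or 5.2% (q = 0.5).

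**5. How far f could go.** Suppose one site at the cap of 40 of 120 takes the looser parse, and failures are spread evenly over patients. Then f is at most about one third of the share of failures that are whole-system replacements before consent. Reaching f = 4% needs about 3 × 4% = 12% of all failures to be of that kind. If the share is 10%, f is 3.3%, the observed rate at q = 1 is 0.8 / (1 − 0.2 × 0.0333) = 80.5%, and the chance of passing is 2.35%.

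**The case for a change.** The best case for a change is that sites apply a criterion as written, and the better reading is an inference from other sections. Protocol 12.1.9 lists enrolling an ineligible subject as a major deviation and prohibits waivers, so a cautious site has a reason to exclude. Protocol 12.1.1.2 expects patients who cannot consent before treatment to be fairly common. Source review under Protocol 12.1.6 comes after the last patient's data collection, perhaps too late to correct differing practice. With q = 1, about one patient screened out per 110 analysed (f = 5%) takes the error above 2.5%. A clarifying clause would need no new data.

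Much of this is true as description: the wording is loose and a misreading is possible. It does not show that a misreading is likely, since the site would also have to pass over 6.5 and the replacement fields on its own forms. Nor does it show which way any bias would run. The loss would not be wholly hidden either. All consented patients receive a study number before screening (Protocol 6.3), Protocol 10 calls for the date and reason of a premature end, and SAP 8.2.1 gives screened and enrolled counts by centre.

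The question about 6.5 failures stands in part. The note repeated in SAP 8.9.1 gives documented device deficiencies affecting drainage as an example of unanticipated drainage, which covers a replacement made for that reason. A change of make for another reason is left open. Since 6.5 already calls these patients failures, an analyst has an obvious starting point.

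**Conclusion.** The concern identifies a real looseness in wording but does not call for a change. Taken as a whole, the protocol keeps replaced patients in, whether the replacement came before or after consent. On that reading the conflict disappears and the effect on the primary result is nil.

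A bias needs three things together: a site taking the less natural parse, whole-system replacements before consent in sufficient number, and a failure rate among those patients above the overall rate. The documents give no figure for the last two. The chances of passing between 1.3% and 15.5% illustrate assumed values of f and q and do not estimate this registry; the upper figure needs a quarter of all failures to be screened out and no successes with them.

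The sponsor can settle the reading in an answer to a site query. A protocol amendment across up to 15 sites would only write down what 6.5 and the endpoint text already largely indicate.

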9.4.1 Anticipated Adverse Device Effects

Complications which may result from the use of the EVD systems include the risks associated with the medications and methods utilized in the surgical procedure, as well as the patient's degree of intolerance to any foreign object implanted in the body.

The principal complications associated with cerebrospinal fluid drainage are Catheter obstruction, infection (including meningitis and ventriculitis), intracranial hypotension/hypertension, migration of ventricular Catheters, ventricular collapse, and intracerebral hemorrhage.

Excessive lowering of ICP in infants may result in complications which include subdural hematomas, markedly sunken fontanelles, overriding of cranial bones, and conversion of a communicating to a non-communicating hydrocephalus.

Ventricular Catheters may be obstructed by particulate matter such as blood clots, fibrin, or brain fragments. If not properly located in the lateral ventricle, the ventricular Catheter may become embedded in the ventricular wall or choroid plexus. Less commonly, the ventricular Catheter may be obstructed by the excessive reduction of ventricular size to slit like proportions.

Complications that are specific for the use of the Cranial Access Kits are improper use of the hand drill including failure to properly secure the drill bit to the variable chuck or failure to properly secure the depth guard to the drill bits. Improper use of the hand drill may result in serious injury. Bleeding may occur at the site of the drill hole, originating from the scalp, bone, dural, or cerebral areas. Due to the possibility of cerebral or extra cerebral hemorrhage or any other complication of this procedure, drill hole placement is the sole responsibility of the attending neurosurgeon.

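### The sepsis exclusion has no time anchor although screening may follow implantation, so a patient with active drain-related sepsis at screening could be lost from the safety data

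*Protocol*

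**What the plan says.** **Eligibility.** Protocol section 6.2, repeated in the synopsis, lists sepsis as criterion 2: "The Patient has sepsis". Criterion 8 is also undated: "The Patients known to have uncorrected coagulopathy". Criterion 4, by contrast, concerns "signs of scalp infection prior to implantation that would be contraindicated per the IFU", and criterion 9 is tied to the time before a Bactiseal catheter is implanted.

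**Timing of screening.** Section 6.3 states that "All consented patients are assigned a study identification (ID) number and screened for eligibility in the study" and that "informed consent is obtained prior or after the start of treatment with the devices". It sets out three routes: consent before implantation, consent while the drain is in use, and consent after the drain is no longer needed. It limits data collection to patients who have met all eligibility criteria.

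**Consequence of failing a criterion.** Section 6.5 makes a consented patient who fails a criterion at screening a screen failure. Protocol 11.3 and SAP 7.3 define the ITT population as consented patients considered to meet all criteria, and the FAS as those of them who had a procedure. SAP 8.10 presents all safety summaries on the FAS.

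**Event recording.** Section 9.7 starts adverse event recording at device implant. Section 9.6 treats any condition present when the subject is screened as baseline and not as an event, unless it later deteriorates.

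**The concern.** Infection is one of the principal complications of CSF drainage in Protocol 9.4.1, and the synopsis names it with hemorrhage as the most common complications. Device- or procedure-related adverse events are the first safety endpoint.

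If eligibility is judged on the day of screening and that day falls after implantation, an outcome of the drain can act as a reason for exclusion. A severe infectious course would then remove the patient from the dataset meant to record it. On the safety side the loss runs one way, towards a more favourable device profile. It comes from the eligibility rule itself, so it would persist at a site that approaches every patient.

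The same gap lets in a patient who was septic at implantation and has recovered by the time of consent.

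**Working it through.** No figure in the plan bears on this point, so the check has two parts: a reading of the sections side by side, and a hypothetical calculation.

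**1. Does the text lead there?** Take a patient without sepsis at implantation who develops a drain infection with sepsis and is approached for consent while septic.

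- Section 6.3 permits consent at this point, and screening follows it.
- On a present-tense reading of criterion 2, the patient fails, and section 6.5 makes the patient a screen failure.
- Protocol 11.3 and SAP 7.3 then keep the patient out of the ITT population and the FAS, and SAP 8.10 keeps the event out of the safety summaries.
- Record review from the index procedure (sections 8.3 and 9.6) does not help, because it applies to patients who are in the registry.

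No section of the protocol or SAP says that criterion 2 is judged as of implantation.

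**2. What if a site admits the patient anyway?** The baseline rule in 9.6 would class the sepsis as pre-existing, since it was present at screening. Section 9.7, and the opening of 9.6 itself, call for events from implant onwards. The two rules give different answers for the same patient.

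**3. Who is affected?**

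| Situation | Effect of the missing anchor |
|---|---|
| Screened before implantation, septic later | None: patient stays in, sepsis is an adverse event |
| Screened after implantation, never septic | None |
| Screened after implantation, drain-related sepsis already resolved | Eligible on the present-tense reading; event recorded from implant |
| Screened after implantation, drain-related sepsis active | Could be screened out |
| Septic at implantation, recovered by a late screening | Could be admitted |

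**4. Hypothetical size.** Let *s* be the true share of otherwise eligible patients who develop drain-related sepsis, and *f* the share of those in whom it is active when they are screened. *f* cannot exceed the share of these patients consented after implantation. Of *N* such patients, *Ns* become septic, *Nsf* are screened out, and *N*(1 − *sf*) remain with *Ns*(1 − *f*) cases. The observed share is

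*s*(1 − *f*) / (1 − *sf*).

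With *s* = 5% and *f* = 50%: 0.05 × 0.5 / (1 − 0.025) = 0.025 / 0.975 = 2.6%.

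Both inputs below are assumed throughout.

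| True share *s* | *f* = 25% | *f* = 50% | *f* = 100% |
|---|---|---|---|
| 2% | 1.5% | 1.0% | 0% |
| 5% | 3.8% | 2.6% | 0% |
| 10% | 7.7% | 5.3% | 0% |

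In the planned 120 patients, *s* = 5% means 6.0 expected cases. The expected number seen becomes 4.6, 3.1 or 0 across the three columns. The last column is a limit, since it needs every such patient to be screened while septic.

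**The case against.** The strongest reply is that the list can be read as conditions before implantation. Criterion 4 refers to the IFU, section 6.4 aims to match the IFU's intended population, and section 9.7 records events from implant. A sensible site may already judge sepsis that way. This stands as far as it goes: exclusion of a drain-related septic patient is a possible reading, not a certain one. But two criteria in the same list carry a date and this one does not, so sites can resolve it differently.

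Four stronger readings are tempting and are not supported:

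- **That the criterion misfires for every patient consented after implantation.** It matters only where sepsis status changed between implantation and screening.
- **That drain infections in general are lost.** Section 9.4.1 names meningitis and ventriculitis, not sepsis. Either of these without sepsis does not trigger criterion 2.
- **That the primary endpoint is biased too.** Section 3.3 gives excessive, variable or inconsistent drainage and device deficiencies as examples of failure. Sepsis is not among them, so this would need the added assumption that septic patients are drainage failures.
- **That criteria 5 and 8 do the same damage.** The documents do not list coagulopathy as a device effect, so criterion 8 shares the drafting gap but not the mechanism. Criterion 5 reads "The Patient is otherwise determined by the Investigator to be medically unsuitable for participation in this Registry". It concerns suitability for the registry and is left to the investigator's judgement, so no rewording of it follows from this point.

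Section 12.1.1.2 expects that patients will fairly often be unable to consent before treatment. It also allows a legally authorized representative to consent. It therefore does not show how often consent falls after implantation.

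**Conclusion.** The concern holds for the timing of the sepsis criterion. As written, the rule can remove a patient with active drain-related sepsis from the FAS and from every safety summary, and can admit a patient whose sepsis preceded the drain. The screening-based baseline rule in 9.6 points the same way and conflicts with event recording from implant in 9.7.

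The text supports that this could happen. It does not show that it will, or how often. The documents give no sepsis rate, no share consented late and no distribution of time from implantation to screening. The 5% to 2.6% example shows the direction and the kind of change possible under assumed inputs; it is not an estimate. The conclusion is confined to the safety endpoint and to patients screened after implantation.

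**What to change.** In the next amendment:

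1. In the synopsis and section 6.2, state that criterion 2, and criterion 8 for consistency, is assessed as of the time before EVD implantation, from the pre-implantation record, whatever the date of consent.
2. Add that conditions arising after implantation are adverse events and not grounds for exclusion.
3. In section 9.6, define baseline by the state at implantation instead of at screening, so that it agrees with 9.7. Check SAP 8.10.1 against the same date, since it counts events from subject enrollment.
4. Report screen failures by reason and by timing of consent (before implantation, during drainage, after). SAP 8.2.1 currently gives the number screened, and reasons only for discontinuations after enrollment.

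This changes when eligibility is judged. Which conditions exclude a patient stays as it is and remains the sponsor's decision.

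The cost is a few sentences, plus a reason and two dates for each screen failure. Patient records are already the data source. A few sicker patients would be retained, so reported safety rates may be less favourable. Rewording cannot bring back patients already screened out, and the documents do not give enrollment status; item 4 would show whether any were lost this way.
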